### 9.2.3 Urinalysis

Routine urinalysis (glucose, protein, blood, nitrite, pH) and 24-hour urine collections for quantitative urinary cystine (Litholink, Chicago, IL) will be performed at regularly scheduled clinic visits as medically needed and at the discretion of the investigator. Urinary metabolomic and metallomic profiles will be performed on urine collected at regularly scheduled clinic visits. No additional urinalysis studies will be collected outside of their normal routine medical care.

## 10 EVALUATIONS BY VISIT

After enrollment into the study, during the initial visit (Visit 1), participants will undergo a complete medical history and physical exam by either the investigator or a sub investigator who is a physician. Blood and urine will be collected if medically necessary as determined by the study investigator to perform blood chemistry profiling, urinalysis, and quantitative urinary cystine, as part of routine management for cystine stone patients. Leftover blood and urine specimens will be collected for further analysis in this study. Additionally, quality of life survey with the Wisconsin Stone-QoL will be performed for research purposes.

As per normal clinical care, at subsequent visits, study participants will be seen every 4 months to obtain serum labs (CBC, chemistries, BUN, creatinine) if medically necessary as determined by the study investigator and 24-hour urine studies (quantitative urinary cystine level). Routine medical management will be continued in all participants, which includes hydration, lowering of dietary sodium intake, and urinary alkalinization.

Plain KUB x-ray with renal ultrasound will be performed on a routine basis if medically necessary as determined by the study investigator. CT scans will also be performed only if medically necessary. These imaging studies will document stone size, location, and any interval changes in stone burden between study visits. No additional visits will be scheduled outside their normal clinical care. These are part of routine evaluation for patients with cystinuria that has been undertaken at UCSF for over 20 years.

At the 36-month visit, in addition to the routine surveillance information collected as noted above, a low-dose non-contrast CT scan of the abdomen will be performed to obtain the data of silent stone recurrence which is one of the primary endpoints in this study.

After the 36-month treatment period, study participants will stop administration of ALA or placebo. They will be seen an additional 24 months at a 4-month interval to obtain routine studies, including serum labs, imaging (plain KUB x-ray and renal ultrasound), and 24-hour urine if medically necessary as determined by the study investigator.

### 10.1 Visit 1 (Initial Visit)

1. Review the study with the participant (participant's legal representative) and obtain written informed consent and HIPAA authorization.
2. Assign the participant a unique study ID number.

3. Record demographics data.
4. Record medical history, including a history of stone disease and family history of stone disease, date of first diagnosis, and prior surgical interventions.
5. Record concomitant medications.
6. Perform a complete physical examination and record vital signs if possible
7. Administer the Wisconsin Stone-QoL survey.
8. Collect routine blood for clinical laboratory tests (CBCs, chemistries, BUN, creatinine) if medically necessary as determined by the study investigator
9. Perform routine 24hr urine testing.
10. Collect passed stone specimens, if presented.
11. Collect discarded blood and urine specimens for research purposes if presented.

### **10.2 Visit 2-9 (every 4th month)**

1. Record any Adverse Experiences and/or Review participant diary for adverse experiences and dosing compliance.
2. Concomitant medications review.
3. Perform pill count.
4. Perform abbreviated physical examination and record vital signs if possible
5. Administer the Wisconsin Stone-QoL survey.
6. Collect routine blood for clinical laboratory tests (CBCs, chemistries, BUN, creatinine) if medically necessary as determined by the study investigator.
7. Perform routine 24hr urine testing.
8. Perform routine KUB x-ray and renal ultrasound if medically necessary as determined by the study investigator.
9. Perform CT scan if medically necessary as determined by the study investigator.
10. Collect passed stone specimens, if presented.
11. Collect discarded blood and urine specimens for research purposes if presented.

### **10.3 Visit 10 (month 36)**

1. Record any Adverse Experiences and/or Review participant diary for adverse experiences and dosing compliance.
2. Concomitant medications review.
3. Perform pill count.
4. Perform abbreviated physical examination and record vital signs if possible
5. Administer the Wisconsin Stone-QoL survey

6. Collect routine blood for clinical laboratory tests (CBCs, chemistries, BUN, creatinine) if medically necessary as determined by the study investigator
7. Perform routine 24hr urine testing.
8. Perform low-dose CT scan for research purposes.
9. Collect passed stone specimens, if presented.
10. Collect discarded blood and urine specimens for research purposes if presented

#### **10.4 Visit 11-16 (every 4th month to 5 years mark)**

1. Record any Adverse Experiences and/or Review participant diary for adverse experiences.
2. Concomitant medications review.
3. Perform abbreviated physical examination and record vital signs if possible
4. Administer the Wisconsin Stone-QoL survey.
5. Collect routine blood for clinical laboratory tests (CBCs, chemistries, BUN, creatinine) if medically necessary as determined by the study investigator
6. Perform routine 24hr urine testing.
7. Perform routine KUB x-ray and renal ultrasound if medically necessary as determined by the study investigator
8. Perform CT scan if medically necessary as determined by the study investigator.
9. Collect passed stone specimens, if presented.
10. Collect discarded blood and urine specimens for research purposes if presented.

#### **10.5 Early Withdrawal Visit**

1. Record any Adverse Experiences and/or Review participant diary for adverse experiences and exclusionary medication use.
2. Concomitant medications review.
3. Perform pill count.
4. Perform abbreviated physical examination and record vital signs if possible
5. Administer the Wisconsin Stone-QoL survey.
6. Collect routine blood for clinical laboratory tests (CBCs, chemistries, BUN, creatinine) if medically necessary as determined by the study investigator
7. Perform routine 24hr urine testing.
8. Perform routine KUB x-ray and renal ultrasound if medically necessary as determined by the study investigator
9. Perform CT scan if medically necessary as determined by the study investigator.
10. Collect passed stone specimens, if presented.
11. Collect discarded blood and urine specimens for research purposes if presented.

## 11 ADVERSE EXPERIENCE REPORTING AND DOCUMENTATION

### 11.1 Adverse Events

An adverse event (AE) is any untoward medical occurrence in a clinical investigation of a participant administered a pharmaceutical product and that does not necessarily have a causal relationship with the treatment. An AE is therefore any unfavorable and unintended sign (including an abnormal laboratory finding), symptom or disease temporally associated with the administration of an investigational product, whether or not related to that investigational product. An unexpected AE is one of a type not identified in nature, severity, or frequency in the current Investigator's Brochure or of greater severity or frequency than expected based on the information in the Investigator's Brochure.

The Investigator will probe, via discussion with the participant, for the occurrence of AEs during each participant visit and record the information in the site's source documents. Adverse events will be recorded in the participant CRF. Adverse events will be described by duration (start and stop dates and times), severity, outcome, treatment and relation to study drug, or if unrelated, the cause.

#### AE Severity

The National Cancer Institute's Common Terminology Criteria for Adverse Events (CTCAE) Version 3.0 should be used to assess and grade AE severity, including laboratory abnormalities judged to be clinically significant. The modified criteria can be found in the study manual. If the experience is not covered in the modified criteria, the guidelines shown in Table 1 below should be used to grade severity. It should be pointed out that the term "severe" is a measure of intensity and that a severe AE is not necessarily serious.

**Table 1. AE Severity Grading**

Severity (Toxicity Grade)	Description
Mild (1)	Transient or mild discomfort; no limitation in activity; no medical intervention or therapy required. The participant may be aware of the sign or symptom but tolerates it reasonably well.
Moderate (2)	Mild to moderate limitation in activity, no or minimal medical intervention/therapy required.
Severe (3)	Marked limitation in activity, medical intervention/therapy required, hospitalizations possible.
Life-threatening (4)	The participant is at risk of death due to the adverse experience as it occurred. This does not refer to an experience that hypothetically might have caused death if it were more severe.

#### AE Relationship to Study Drug

The relationship of an AE to the study drug should be assessed using the following the guidelines in Table 2.

**Table 2. AE Relationship to Study Drug**

Relationship to Drug	Comment
Definitely	Previously known toxicity of agent; or an event that follows a reasonable temporal sequence from administration of the drug; that follows a known or expected response pattern to the suspected drug; that is confirmed by stopping or reducing the dosage of the drug; and that is not explained by any other reasonable hypothesis.
Probably	An event that follows a reasonable temporal sequence from administration of the drug; that follows a known or expected response pattern to the suspected drug; that is confirmed by stopping or reducing the dosage of the drug; and that is unlikely to be explained by the known characteristics of the participant's clinical state or by other interventions.
Possibly	An event that follows a reasonable temporal sequence from administration of the drug; that follows a known or expected response pattern to that suspected drug; but that could readily have been produced by a number of other factors.
Unrelated	An event that can be determined with certainty to have no relationship to the study drug.

## **11.2 Serious Adverse Experiences (SAE)**

An SAE is defined as any AE occurring at any dose that results in any of the following outcomes:

- death
- a life-threatening adverse experience
- inpatient hospitalization or prolongation of existing hospitalization
- a persistent or significant disability/incapacity
- a congenital anomaly/birth defect

Other important medical events may also be considered an SAE when, based on appropriate medical judgment, they jeopardize the participant or require intervention to prevent one of the outcomes listed.

### **11.2.1 Serious Adverse Experience Reporting**

Study sites will document all SAEs that occur (whether or not related to study drug) per [UCSF CHR Guidelines](#). The collection period for all SAEs will begin after informed consent is obtained and end after procedures for the final study visit have been completed.

In accordance with the standard operating procedures and policies of the local Institutional Review Board (IRB)/Independent Ethics Committee (IEC), the site investigator will report SAEs to the IRB/IEC.

## 12 DISCONTINUATION AND REPLACEMENT OF PARTICIPANTS

### 12.1 Early Discontinuation of Study Drug

A participant may be discontinued from study treatment at any time if the participant, the investigator, or the Sponsor/Investigator feels that it is not in the participant's best interest to continue. The following is a list of possible reasons for study treatment discontinuation:

- Participant withdrawal of consent (or assent)
- Participant is not compliant with study procedures
- Adverse event that in the opinion of the investigator would be in the best interest of the participant to discontinue study treatment
- Protocol violation requiring discontinuation of study treatment
- Lost to follow-up
- Sponsor request for early termination of study
- Positive pregnancy test (females)

If a participant is withdrawn from treatment due to an adverse event, the participant will be followed and treated by the Investigator until the abnormal parameter or symptom has resolved or stabilized.

All participants who discontinue study treatment should come in for an early discontinuation visit as soon as possible and then should be encouraged to complete all remaining scheduled visits and procedures.

All participants are free to withdraw from participation at any time, for any reason, specified or unspecified, and without prejudice.

Reasonable attempts will be made by the investigator to provide a reason for participant withdrawals. The reason for the participant's withdrawal from the study will be specified in the participant's source documents (Refer to Section 10) for early termination procedures.

### 12.3 Withdrawal of Participants from the Study

A participant may be withdrawn from the study at any time if the participant, the investigator, or the Sponsor feels that it is not in the participant's best interest to continue.

All participants are free to withdraw from participation at any time, for any reason, specified or unspecified, and without prejudice.

Reasonable attempts will be made by the investigator to provide a reason for participant withdrawals. The reason for the participant's withdrawal from the study will be specified in the participant's source documents. As noted above, participants who discontinue study treatment early (i.e., they withdraw prior to Visit 4) should have an early discontinuation visit. Refer to Section 10 for early termination procedures. Participants who withdraw after Visit 1 but prior to Visit 4 should be encouraged to come in for a final visit (and the procedures to be followed would include those for their next scheduled visit).

#### **12.4 Replacement of Participants**

Participants who withdraw from the study treatment will not be replaced.

Participants who withdraw from the study will not be replaced.

### **13 PROTOCOL VIOLATIONS**

A protocol violation occurs when the participant, investigator, or FDA fails to adhere to significant protocol requirements affecting the inclusion, exclusion, participant safety and primary endpoint criteria. Protocol violations for this study include, but are not limited to, the following:

- Failure to meet inclusion/exclusion criteria
- Use of a prohibited concomitant medication
- Failure to orally intake prescribed dosage on a daily basis
- Intake of ALA supplement exceeds the prescribed daily dosage

Failure to comply with Good Clinical Practice (GCP) guidelines will also result in a protocol violation. The FDA will determine if a protocol violation will result in withdrawal of a participant.

When a protocol violation occurs, it will be discussed with the investigator and a Protocol Violation Form detailing the violation will be generated. This form will be signed by a Sponsor representative and the Investigator. A copy of the form will be filed in the site's regulatory binder and in the Sponsor's files.

### **14 DATA SAFETY MONITORING**

The study investigator will work with the study team to ensure that participants' privacy and information is protected. They both have access to experienced clinical trials offices and expertise in conducting clinical research similar to the one proposed in this application, ensuring that safe and ethical practices will be followed. Physical risk will be minimized by the study design since routine clinical care will not be altered with inclusion in this study. All health-system source/legacy data files will be stored at the UCSF local health system and will be accessed only by the programmers/analysts working on this study. Since confidential information will be collected from the medical charts, we will not directly link personal identifiers with the data collected nor will we

use personal identifiers in any reports, materials, or presentations that emanate from this work. All electronic files containing personal identifiers will be stored only on the UCSF site file servers located behind a firewall. Information transferred to the server for backup purposes will be done via secure ftp. Files may be transferred to other computers temporarily via the Internet to facilitate central upload. In these circumstances, the files will be protected by encryption. The UCSF site file servers are only accessible by network support specialists working in secure locations. The on-site file server will be electronically accessible only to study investigators through user password protection. Access to study data is protected and participant to the same security protections as other confidential health system data. Computer passwords are changed on a regular basis. Individual identifiers such as names and medical record numbers will be removed from study data files in the data processing steps and will not be accessible to collaborators accessing the database for further study as described in this study application.

The participating collaborators will maintain a data link from the study data but not to the personal identifiers (to permit reanalysis of the data files). In addition, all investigators and support staff involved with collection or entry of clinical data are HIPAA certified and have completed and are current with regard to IRB training. Investigators and project staff will sign confidentiality pledges annually HIPAA training annually. Datasets shared with external collaborators will be stripped of any identifying information according to HIPAA policy.

## **15 STATISTICAL METHODS AND CONSIDERATIONS**

Prior to the analysis of the final study data, a detailed Statistical Analysis Plan (SAP) will be written describing all analyses that will be performed. The SAP will contain any modifications to the analysis plan described below.

### **15.1 Data Sets Analyzed**

Data sets from all participants enrolled in the study will be analyzed.

The primary efficacy endpoint will be assessed by medical history and physical exam, in addition to radiographic imaging performed at each study visit.

The secondary efficacy endpoints will be assessed by 24-hour urine collections (Litholink, Chicago, IL), and the analysis of the metallomic and metabolomics profiles of urine and stone samples that are collected.

### **15.2 Analysis of Primary Endpoint**

The primary efficacy endpoint will be assessed in two ways over the course of the 3-year treatment period: 1) symptomatic stone recurrences, defined as renal colic, stone passage, or surgical removal of a stone; and 2) silent stone recurrences classified as stone growth or new stones, diagnosed on the basis of renal ultrasound, plain KUB x-ray, or if clinically indicated, CT scan. The analysis will be performed on the intention-to-treat principle in the treatment and placebo groups.

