PRIMARY ENDPOINT	
The primary efficacy endpoint will be assessed in two ways over the course of the 3-year treatment period:
 
 
1) symptomatic stone recurrences, defined as renal colic, stone passage, or surgical removal of a stone;
 
2) silent stone recurrences, classified as stone growth or new stones,
 

	diagnosed on the basis of renal ultrasound, plain KUB x-ray, or if clinically indicated, computed tomography.
SAFETY EVALUATIONS	After participants are enrolled at 3-4 weeks during the treatment period, a study coordinator will contact each participant to check compliance, tolerability, and side effects with ALA supplementation. Any concern for a potential adverse event will be reviewed by the study investigators. Patient clinical care will continue as per the current standard for the duration of this study. Tolerability and side effects will be reviewed at each scheduled clinic visit which normally occur every four months. All reported adverse events will be reviewed by the study investigators. Depending on the severity of the adverse event, the study investigator may determine the need for un-blinding, and the participant may be advised to stop ALA intake if it is determined that ALA is the cause.
PLANNED INTERIM ANALYSES	When 50% of target participants have been enrolled and on the study protocol for 6 months, an interim analysis will be performed by an un-blinded statistician to evaluate for ALA clinical effects.
STATISTICS Primary Analysis Plan	The analysis will be performed on the intention-to-treat principle in the treatment and placebo groups. The primary efficacy endpoint will be assessed by comparing the rates of symptomatic and silent stone recurrences using the t-test with a two-sided p-values and calculated 95% confidence intervals. In addition, the analysis of secondary endpoints will compare quantitative urinary cystine, and metallomic and metabolomics profiles using repeated measures of analysis of variance.

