Rationale for Number of Participants	The target enrollment for this study is 50 participants, based on a conservative approach to determine the sample size needed to evaluate the effect of ALA supplementation. Two recent studies evaluating the medical management of cystinuric individuals have reported that among individuals who are compliant in taking medications, the average number of stone events per person is approximately 1 per year (Reference #'s 5, 9). The current study design will be powered at 90% to detect a clinically meaningful reduction of stone events at 50% (0.5 stone events per year) with two-tailed $\alpha = 0.05$ . Based on a two-sided t-test, the following scenarios were considered for the standard deviation (SD) for the sample and sample size (n): SD 0.5, n=11; SD 0.75, n=24; SD 1, n=42. To account for a small dropout rate over the study duration, the enrollment goal of 50 participants was proposed.

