Clinical data including medical history, plain KUB x-ray and renal ultrasound, routine blood work, and 24-hour urine collections for all participants will be collected as part of normal clinical care at routine clinical visit intervals, which currently occur every 4 months. Routine clinical care for participants will not be altered in any way outside of administration of the supplement or placebo. Routine clinical care generally consists of office visits every 4 months at which time, as medically necessary as determined by the study investigator, an imaging study is performed (plain KUB x-ray, ultrasound, or CT scan if clinically indicated), a 24-hour urine collection is done to check quantitative urinary cystine levels, and blood is drawn to evaluate electrolyte levels as well as renal function. During routine visits for blood and urine tests, any discarded blood and urine specimens will be collected for research testing. No additional blood draw or urine collection will be performed for this study. From discarded routine specimens provided during these clinic visits, metallomic and metabolomics profiling will be performed for all participants using discarded samples material. This is comprised of mass spectrometry and elemental analysis of samples performed in our research lab. Quality of life measurement, as recorded by the Wisconsin Stone-quality of life questionnaire (Wisconsin Stone-QoL), will also be evaluated.

Recurrent stone events, defined by symptomatic or silent stone recurrence, is the primary endpoint in this study. It will be documented in this study cohort, and compared between treatment and placebo groups to determine treatment effect. If stones are removed for surgery or spontaneously passed by participants, any discarded stone specimens not needed for clinical care will also be subjected to metabolomic and metallomic analysis.

At the end of the three years of study drug treatment, all participants will undergo a low dose non-contrast CT scan to look for a silent change in stone size. As this is a pilot study, recruitment will be limited to target enrollment of 50 participants (25 for each treatment arm). Treatment will continue for a total of 3 years and after treatment completion, participants will be followed for an additional 2 years to evaluate for change in clinical status or adverse events resultant from ALA administration.

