### 15.3 Sample Size and Randomization

The target enrollment for this study is 50 participants, based on a conservative approach to determine the sample size needed to evaluate the effect of ALA supplementation. Two recent studies evaluating the medical management of cystinuric individuals have reported that among individuals who are compliant in taking medications, the average number of stone events per person is approximately 1 per year (Reference #'s 5, 9). The current study design will be powered at 90% to detect a clinically meaningful reduction of stone events at 50% (0.5 stone events per year) with two-tailed  $\alpha = 0.05$ . Based on a two-sided t- test, the following scenarios were considered for the standard deviation (SD) for the sample and sample size (n): SD 0.5, n=11; SD 0.75, n=24; SD 1, n=42. To account for a small dropout rate over the study duration, the enrollment of 50 participants was proposed. At UCSF, clinical volume approximates 60 nephrolithiasis patients per week, including those with cystinuria. At a recent cystinuria outreach event led by [name] at UCSF (<http://[name].ucsf.edu/?q=news/june-18-2015-cystine-patient-symposium>), over 50 individuals with cystinuria attended among over 100 participants overall. We anticipate that 6-8 months will be required to accrue these participants.

Participants will be computer sequence-randomized to receive either ALA or placebo.

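### The primary endpoint is one composite in section 4.1 but can be read as two endpoints elsewhere, and no rule says which result decides success; if either of two tests at 0.05 sufficed, the error would be about 8-10%

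*Combined protocol and SAP*

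**What the plan says.** **One endpoint.** Section 4.1: "Recurrent stone events, defined by symptomatic or silent stone recurrence, is the primary endpoint in this study". Section 15.3 fits this. It takes one planning figure, "the average number of stone events per person is approximately 1 per year", and states that the trial is "powered at 90% to detect a clinically meaningful reduction of stone events at 50% (0.5 stone events per year"), at a two-tailed alpha of 0.05. That alpha is given for the sample size (section 15.3 and the synopsis rationale) and is not divided between endpoints.

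**One endpoint with two parts.** Sections 5.1 and 15.2 and the synopsis endpoint row keep the singular: "The primary efficacy endpoint will be assessed in two ways over the course of the 3-year treatment period". The parts are symptomatic recurrence (colic, passage or surgical removal) and silent recurrence (growth or new stones on imaging). Section 15.2 names no test.

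**More than one endpoint.** Section 10 justifies the month-36 CT scan by "silent stone recurrence which is one of the primary endpoints in this study". The synopsis, the only place that names a primary test, plans "comparing the rates of symptomatic and silent stone recurrences using the t-test with a two-sided p-values and calculated 95% confidence intervals".

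**Decision rule.** None is given: no hierarchy, no alpha split, no requirement that both parts be positive. Sections 5.2 and 8.2 let the investigators end the trial early if the interim analysis shows significantly better clinical outcomes on ALA, without naming the outcome or a boundary. Section 15 defers detail to a later SAP, due before the final data are analysed.

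**The concern.** A reader cannot tell from the plan whether the trial has one confirmatory test or two. The choice sets the false-positive rate. With one test on the composite, the 5% used for the sample size is the error of the final analysis. With two tests and success on either, it is not. Because no section fixes the choice, it could be made after the results are seen, and at the interim look it could be made by whoever judges that outcomes have significantly improved.

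Two related gaps follow. The planning rate of about 1 event per year is not identified as symptomatic, silent or both, so the 90% power claim is not tied to a defined outcome. There is also no counting rule for a stone that is seen to grow on imaging, then causes colic, then passes or is removed. The plan compares rates, so the count per person has to be defined.

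**Working it through.** **1. The plan's own figures.** The documents state no family-wise error, only alpha 0.05 within a sample-size calculation for one outcome. Inputs from section 15.3: difference 0.5 per year, SD 0.5, 0.75 or 1, 90% power. The stated n of 11, 24 and 42 equal (SD × (1.960 + 1.282) / 0.5)² = 10.5, 23.6 and 42.03. That is a one-sample formula. The two-sample formula doubles these to 21.0, 47.3 and 84.06, so 22, 48 and 85 per arm. The discrepancy is a separate point. What matters here is that only one outcome and one alpha enter.

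**2. Error under each reading of the endpoint** (final analysis only, no true effect on either component)

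Let Z1 and Z2 be the two component test statistics with correlation r. The documents do not give r, so a range is shown.

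- Composite only, one test: 5%.
- Both components must be significant: at most 5%.
- Either suffices, each at two-sided 0.05: 1 − P(|Z1| < 1.96 and |Z2| < 1.96). At r = 0 this is 1 − 0.95² = 0.0975.

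| r | error if either suffices |
|---|---|
| 0 | 9.75% |
| 0.3 | 9.5% |
| 0.5 | 9.1% |
| 0.7 | 8.3% |
| 0.77 | 8.0% |
| 0.8 | 7.8% |
| 0.9 | 7.0% |

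The 8-10% range therefore needs r no higher than about 0.77.

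**3. Is that range of r plausible?** t-tests were simulated with 25 per arm, 3 years, 1 event per year in total, half of it silent, and a patient-level frailty shared by both components (the split and the frailty are assumptions). The error was 9.2-9.5% when the SD of the annual rate was about 0.6 to 0.9. It fell to 7.4% only at an SD of 1.5, above the largest SD in the plan.

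**4. The interim look.** No boundary is stated. If the interim were also tested at 0.05, with 8% to 50% of the information available (assumption), one composite would carry 8.3-9.5% overall. Two endpoints with either sufficing would carry about 15-18% (r from 0 to 0.5).

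**5. Cost of the remedies at 25 per arm** (SD 0.5 / 0.75 / 1)

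- Single composite at 0.05, t-test: power 93 / 64 / 41%, unchanged from the present design.
- Alpha split, 0.025 each: error 0.0494 at r = 0 and 0.0465 at r = 0.5. Power by normal approximation falls from 94 / 65 / 42% to 90 / 55 / 32%, if the 0.5 difference and these SDs applied to each component.
- Fixed order with symptomatic events first: if 1 per year covers all events and a share s is symptomatic (assumption; variance proportional to rate), the standardised difference becomes 0.5s / (SD × √s). Power is 85 / 52 / 32% at s = 0.75 and 69 / 37 / 23% at s = 0.5.

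**The case against.** The best defence is that most of the text fits one endpoint ascertained by two routes. Sections 4.1, 5.1 and 15.2 use the singular, the sample size uses one rate, and the synopsis sentence could mean a combined rate. On that view the plural in section 10 is a slip and the error is 5%. The study is also called a pilot, and a later SAP is promised.

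Much of this stands. It shows that the composite is the natural reading, and it is why the fix below adopts it. It does not supply a decision rule. The synopsis still pairs p-values and intervals with two named rates, and the SAP is required only before the final analysis, whereas the interim look that could close the trial comes earlier.

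Three stronger readings are tempting but not supported:

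- A reader might infer that the trial's error is 8-10%. A per-endpoint alpha of 0.05 is written nowhere. It is inferred from the single alpha and the 95% intervals. Nor does any section say that either result suffices.
- A reader might infer that success may be claimed on whichever of symptomatic, silent or combined is significant. No section plans a test of the composite beside tests of its parts.
- A reader might infer that each manifestation of one stone counts as a separate event. The definition joins colic, passage and removal by *or* and says nothing about counting. Multiple counting is not ruled out, but the documents give no basis for sizing it.

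**Conclusion.** The inconsistency is real and should be resolved before the interim analysis. The documents allow readings whose final-analysis error runs from 5% or less (composite, or both components required) to nearly 10% (either component suffices), and nothing fixes which applies. The 8-10% figure rests on three conditions: two tests each at two-sided 0.05, success on either, and a correlation between the tests of at most about 0.77. The first two are inferred and the third is assumed. It excludes any inflation from the interim look.

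The missing counting rule and the unidentified planning rate are gaps of definition. Their effect cannot be quantified from the documents. In particular, the documents do not show that the rate of 1 per year means symptomatic events.

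**What to change.** 1. In the synopsis and sections 5.1, 10 and 15.2, name the section 4.1 composite as the sole primary endpoint: stone events per person-year, symptomatic or silent, with one test at two-sided 0.05. Report symptomatic and silent recurrence separately as supportive components with confidence intervals.
2. State that the interim efficacy analysis uses this same endpoint. Its boundary needs its own rule, because naming one endpoint does not remove the inflation in step 4 of the working.
3. Add a counting rule: all manifestations of the same stone are one event.
4. After checking the two cited sources, state in section 15.3 and the synopsis which endpoint the 1.0 versus 0.5 per year planning rates describe.
5. If the sponsor prefers two primaries, write a fixed order or an alpha split before the interim analysis, and restate power for the first-ranked endpoint (for a split, for each endpoint at its own alpha).

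Items 1 to 4 cost wording only, and the composite takes no power from the present design. The downside is that neither component can carry a stand-alone primary claim. Item 5 keeps such a claim possible, but at the power cost shown in step 5 of the working.
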